## Synopsis

**Introduction:** Real-time continuous glucose monitoring (rt-CGM) systems provide users with information about current interstitial glucose levels and alert the patient before the upper or lower glucose threshold is reached or when glucose levels change rapidly. Hence, glycaemic excursions can be early identified and accordingly adapted by behavioural change or pharmacologic intervention. Randomized controlled studies adequately powered to evaluate the impact of long-term application of rt-CGM systems on the risk reduction of adverse obstetric outcomes are missing.

**Study Design:** Open-label multicentre randomized controlled trial with two parallel groups including a total of 372 female patients with recent diagnosis of GDM: n=186 with rt-CGM (Dexcom G6), n=186 with self-monitored blood glucose (SMBG). Following the recommendations for the evaluation of complex interventions, a health economic evaluation will be performed.

**Visits:** Women with GDM will be consecutively recruited at their first appointment after diagnosis (V1) and randomized to either treatment (rt-CGM augmented glucose monitoring) or control group (routine care SMBG) after a run-in period of 6-8 days at the second visit (V2). The third visit (V3) will be scheduled 8 to 10 days after V2 and further follow-up visits every two weeks. At every visit glucose measurements (SMBG or rt-CGM) will be evaluated by the medical staff and all patients will be treated according to the standard of care for patients with GDM. From V2 to V3 as well as once for ten days between gestational week 36+0 and 38+6 the control group will receive blinded CGM. Cord blood will be sampled immediately after delivery (VPP0). A postpartum examination will be scheduled within 48 hours after delivery (VPP1) for assessment of neonatal biometry and maternal HbA1c, as well as **between 8 weeks to 12 months** after delivery (VPP2) in all patients for a detailed re-examination of glucose metabolism including blinded CGM for 8 to 10 days in both groups.

**Outcomes:** Differences in the proportion of LGA newborns (birth weight >90. pct) in women with GDM using rt-CGM as compared to women with GDM using SMBG will be assessed as the primary outcome. Differences in neonatal hypoglycemia, rate of caesarean section, shoulder dystocia and neonatal anthropometry will be assessed as secondary outcomes. Further secondary outcomes are: differences in neonatal hyperinsulinemia, CGM measures such as mean interstitial glucose, glucose variability, time in range as well as time spent in hyper- and hypoglycemia (day- and night-time), duration and frequency of postprandial hyperglycaemic excursions, start and amount of glucose lowering therapy, HbA1c, change in bodyweight during pregnancy and after delivery, glucose disposal at postpartum (markers of insulin sensitivity, insulin secretion and  $\beta$ -cell function assessed by a postpartum OGTT), as well as health-related quality of life, and patients' risk- and time preferences and its association with adherence to dietary and exercise recommendations.

## 1. General Conditions

### 1.1. *Scientific background of the study*

The incidence of obesity and diabetes is rising worldwide even in younger populations. With a rise in maternal obesity also gestational diabetes mellitus (GDM) becomes more prevalent with a prevalence of up to 18% of pregnancies. Previous studies found hyperglycaemia in pregnancy to be associated with gestational complications including macrosomia and neonatal hyperinsulinaemic hypoglycaemia and an increased long-term risk for obesity or diabetes in the offspring's later life. Large interventional trials provided evidence that obstetric and neonatal complications such as large for gestational age offspring (LGA, defined as birthweight >90 pct.) or shoulder dystocia can be significantly reduced through intensified treatment of even mild forms of maternal hyperglycaemia (e.g. by lifestyle modification or pharmacotherapy).

Continuous Glucose Monitoring (CGM) has been shown to improve glycaemic control without increasing the risk of hypoglycaemia in patients with type 1 and 2 diabetes. However, only a small number of studies evaluated the use of CGM in pregnancies affected by GDM: In the setting of a larger non-randomized observational study Yu et al. found that mothers in the CGM group (using CGM for 72 hours every 2 to 4 weeks) had improved glycaemic control as well as a lower amount of glycaemic variability as compared to a control group using self-monitored blood glucose (SMBG). In addition, the CGM group showed lower birth weight percentiles associated with a lower risk for LGA offspring (13.7% vs. 25.8) or neonatal hypoglycaemia (5.5% vs. 14%). Also a second observational study including 57 pregnancies with GDM indicated that CGM was more effectively detecting hyperglycaemic episodes as well as nocturnal hypoglycaemia as compared to SMBG. A study in 73 pregnant women with GDM, randomly assigned to either SMBG or CGM for a duration of 48h after diagnosis, found that CGM detected a markedly higher proportion of women requiring glucose lowering pharmacotherapy (31% vs 8%). Another randomized controlled trial on 106 women with GDM observed significantly lower weight gain associated with CGM. LGA cases were more often observed in the SMBG group (52.7% vs. 35.3%), however, the difference failed statistical significance as the study was not powered for obstetric outcomes.

Unfortunately, both randomized controlled studies used older versions of a blinded CGM device, where glucose values are not directly visible for patients. In contrast, more recently developed "real-time" CGM (rt-CGM) systems provide users with information about current glucose levels and alert the patient before the upper or lower glucose threshold is reached or when glucose levels change rapidly. Hence, glycaemic excursions can be rapidly identified and accordingly adapted by behavioural change or pharmacologic intervention. A number of studies including non-pregnant patients have shown superiority of rt-CGM over

older blinded CGM versions in order to effectively empower and educate patients with diabetes to better understand how dietary habits, exercise or pharmacotherapy affects their glucose levels. A beneficial effect of rt-CGM in pregnancy was also supported by the CONCEPTT trial for pregnant women with type 1 diabetes. Only one recent study compared SMBG with rt-CGM in women with GDM using a single application for 3–7 days within two weeks after diagnosis but it failed to demonstrate improvements in HbA1c or pregnancy outcomes, which was, however, likely due to the sample size and the short duration of intervention (single application).

Taken together, larger randomized controlled studies adequately powered to evaluate the impact of long-term application of rt-CGM systems on the risk reduction of adverse obstetric outcomes are missing. Of note, such studies are of high clinical relevance because of their guideline-changing potential. In addition, rt-CGM has the potential to reduce reported barriers to SMBG (such as inconvenience, pain or stigma of testing in public places) in order to improve poor reliability and adherence to glucose monitoring, which is a non-negligible problem in the treatment of GDM.

### *1.2. Specific Hypotheses*

The main hypothesis of the proposed study is that rt-CGM can effectively reduce the risk for neonatal and obstetric complications. It is further hypothesized that rt-CGM can improve maternal glycaemic control, body weight gain during pregnancy and (as rt-CGM potentially improves self-management strategies) has beneficial long-term effects on maternal metabolism after pregnancy.

### *1.3. Primary and secondary outcomes*

*Primary objective:* To assess differences in the proportion of LGA newborns (birth weight >90. pct) in women with GDM using rt-CGM as compared to women with GDM using SMBG.

*Secondary objectives:* To assess differences in further obstetric or neonatal complications, neonatal hypoglycaemia, rate of caesarean section, shoulder dystocia and neonatal anthropometry will be assessed as secondary objectives. Further secondary outcomes are: differences in neonatal hyperinsulinemia, rt-CGM measures such as mean interstitial glucose, glycaemic variability, time in range (65 to 140 mg/dl [3.6 to 7.8 mmol/l]) as well as time spent in hyper- and hypoglycaemia (day-time: 07.01 to 22.59hr and night-time: 23.00 to 07.00hr), duration and frequency postprandial hyperglycaemic excursions, start and amount of glucose lowering therapy, HbA1c, glycosylated fibronectin, hsCRP, proBNP, Troponin T, change in bodyweight during pregnancy and after delivery as well as glucose disposal at postpartum (markers of insulin sensitivity, insulin secretion and β-cell function assessed by a postpartum OGTT). Health-related quality of life (HRQoL) is a patient-reported outcome which has become

as important in the evaluation of interventions as patient-relevant clinical outcomes. Therefore, HRQoL will be elicited. In addition, a health economic evaluation in terms of cost-effectiveness and cost-utility analysis will be performed.

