## 2. Research Design and Methods

### 2.1. Participants and recruitment; Exclusion criteria

This study is designed as an open-label multicentre randomized controlled trial with two parallel groups including a total of 372 female patients (n=186 with rt-CGM, n=186 with SMBG) with recent diagnosis of GDM. Diagnosis of GDM (i.e. diabetes first diagnosed in second and third trimester and not clearly type 1 or type 2 diabetes) is made in accordance with the IADPSG criteria after 24+0 weeks of gestation by a 2h 75g OGTT. If the GDM diagnosis is made before 24+0 weeks of gestation in accordance with the local guideline (i.e. when IADPSG cut-offs for fasting and post-load glucose are exceeded) patients can be included if no insulin treatment was started until 24+0^21. The study will be conducted at four tertiary referral centres in Austria, Switzerland, Sweden and Germany. All pregnant females (aged between 18 and 55 years) will be consecutively recruited after diagnosis of GDM until 31+6 weeks of gestation among women visiting the pregnancy outpatient departments (Division of Obstetrics and feto-maternal Medicine, Medical University of Vienna; Division of Obstetrics, University Hospital Basel, Clinic of Obstetrics, Charité Berlin, Clinic of Obstetrics, University Hospital Jena) or the diabetes outpatient departments (Division of Endocrinology and Metabolic Diseases at the Heinrich Heine University, Düsseldorf; Department of Medicine, University Hospital, Örebro).

Exclusion criteria are:

Overt diabetes (i.e. pregestationally known type 1 or type 2 diabetes or fasting plasma glucose during the OGTT  $\geq 126$  mg/dl [7.0 mmol/l] or HbA1c  $\geq 6.5\%$  [44 mmol/l] or 2h post-load OGTT levels  $\geq 200$  mg/dl [11.1 mmol/l] assessed before 24+0 weeks of gestation, whereby results need to be confirmed by repeated testing in case of unequivocal hyperglycemia according to the ADA standards); History of bariatric surgery or other surgeries that induce malabsorption; Long-term use (>2 weeks) of systemic steroids prior to enrolment; Multiple pregnancy; Patients already using glucose lowering medications (metformin or insulin) before study entry; fetal growth restriction due to placental dysfunction at study entry; Inpatient psychiatric treatment up to 1 year before enrolment; Participation in this study in previous pregnancy;

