## *2.2. Study visits pregnancy*

A broad risk evaluation will be performed in participating females at the initial contact (V1) including: evaluation of maternal age, parity, history of GDM in previous pregnancies, detailed family history, ethnicity, preconceptional diseases, obstetric history. Height (stadiometer measured to the nearest centimeter) and actual weight (calibrated scales, no clothes) will be additionally assessed. Moreover, an evaluation of preconceptional weight (self-reported) and BMI as well as measurement of blood pressure will be performed. All patients receive medical nutrition therapy (isocaloric diet containing 40-50% carbohydrates, 20% proteins and 30-35% fat, divided into three meals and three snacks) and lifestyle advice for 30 minutes following international recommendations and are advised on capillary blood glucose measurement (fasting as well as 1h after starting each meal) at the initial visit (V1). Randomisation will be done after a run-in period of 6 to 8 days (V2). The run-in period is omitted for patients who had a diagnosis of GDM before 24+0 according to the local guidelines and already received medical nutrition therapy, lifestyle intervention and advices on capillary blood glucose measurements. The third visit (V3) will be scheduled 8 to 10 days after V2 and further follow-up visits every two weeks (i.e. 12 to 16 days after each visit). HbA1c and glycosylated fibronectin, hsCRP, proBNP, Troponin T, will be assessed at V2 as well as at the first visit between 36+0 and 38+6 weeks of gestation (12 ml, non-fasting state) (V4). Detailed fetal ultrasound examinations, a detailed examination of dietary intake as well as a blinded CGM (control group only) will be performed at V2 and V4. Body weight change and use of glucose lowering medications (amount of insulin units) will be examined at every visit. At every follow-up visit glucose measurements (SMBG or rt-CGM) and routine ultrasound examinations (fetal biometry and umbilical artery doppler) will be evaluated by the medical staff and all patients will be treated according to the standard of care for patients with GDM. This includes lifestyle modification and insulin therapy if recommended thresholds are exceeded. Both groups will be treated to be in the target range between 65 to 140 mg/dl [3.6 to 7.8 mmol/l] with at least 8h fasting glucose levels equal or below 95 mg/dl [5.3 mmol/l] and 1h postprandial glucose

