### *2.4. Randomisation*

Participants will be randomized to either treatment (rt-CGM augmented glucose monitoring) or control group (routine care SMBG) in a 1:1 ratio. The minimisation method with a 0.85 assignment probability will be used to minimize the imbalance between the groups according to week of gestation at study entry i.e. at V1 (three strata: 24+0 to 25+6, 26+0 to 27+6, 28+0 to 29+6, 30+0 to 31+6), previous pregnancy with GDM (two strata: yes or no) and preconceptional overweight/obesity status with three strata: i. normal weight (i.e. BMI below  $25.0 \text{ kg/m}^2$ ); ii. overweight ( $\text{BMI } 25.0 - 29.9 \text{ kg/m}^2$ ); iii. obesity ( $\text{BMI equal or above } 30.0 \text{ kg/m}^2$ ). Randomisation will be performed at the second study visit (V2) by using the "MUW Randomizer" software.

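### Pregnancy weight change has no defined start or end point, and its default unadjusted test ignores weight and gestational week at randomisation

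*Combined protocol and SAP*

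**What the plan says.** Section 1.2 puts forward the hypothesis that "rt-CGM can improve maternal glycaemic control, body weight gain during pregnancy". Section 1.3, like the Synopsis, lists "change in bodyweight during pregnancy and after delivery" among the secondary outcomes. Neither place says from which weight, to which weight, or over what time the change is taken.

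Section 2.2 describes three sources of weight data. At V1 there is "an evaluation of preconceptional weight (self-reported) and BMI", and in addition "actual weight (calibrated scales, no clothes) will be additionally assessed". After that, "Body weight change and use of glucose lowering medications (amount of insulin units) will be examined at every visit".

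Randomisation is at V2. That is 6 to 8 days after V1, except that the run-in is dropped for women diagnosed before 24+0 who have already been counselled (section 2.2). Women are "consecutively recruited after diagnosis of GDM until 31+6 weeks of gestation" (section 2.1). The minimisation factors in section 2.4 are "week of gestation at study entry i.e. at V1", with a lowest stratum starting at 24+0, previous GDM, and preconceptional BMI class.

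Section 3.2 compares continuous secondary outcomes by Student's t-test, with a rank-based test for skewed data. Maternal weight change is not among the examples listed, but the list is open-ended and no other method is given for it. No covariate enters the comparison.

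**The concern.** rt-CGM can act on weight only after V2. Most of a pregnancy has passed by then, so a change counted from before conception would combine a part that the intervention can influence with a longer part that it cannot. The earlier part, and any error in a recalled weight, would widen the standard error without carrying information about the treatment.

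The time left after V2 also differs greatly between women, and so does the gain that can accrue in it. A test without covariates leaves that variation in the residual.

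At stake is the precision of one named maternal hypothesis. A real effect on weight after V2 could be reported as no clear difference. With several possible starting weights in an open-label trial, the choice of origin could also be made after results are known.

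**Working it through.** **1. The plan's own figure.** There is none for weight. The only sample size is for LGA, in section 3.1: 13.7% against 25.8%, two-sided 0.05, 80% power, Pearson chi-square. With a mean proportion of 0.1975:

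n per arm = [1.96·√(2·0.1975·0.8025) + 0.8416·√(0.137·0.863 + 0.258·0.742)]² / 0.121² = 168.8, so 169 per arm and 338 in total.

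This reproduces the plan. I use 169 evaluable women per arm below.

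**2. When randomisation happens.**
- Earliest: 24+0, without run-in.
- Latest: entry at 31+6 plus 8 days = 33+0.

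**3. Share of gestation before V2.** Birth at 39 weeks is an assumption.
- 24/39 = 62% and 33/39 = 85% precede V2.
- 39 − 24 = 15 and 39 − 33 = 6 weeks remain, a ratio of 15/6 = 2.5.
- With birth at 38 to 40 weeks, the share runs from 24/40 = 60% to 33/38 = 87%, and 5 to 16 weeks remain.

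**4. Cost if the origin were preconceptional weight.** The documents give neither an SD nor an expected effect for weight change, so only a conditional figure is possible. Take the effect on change from V2 that has 80% power at 169 per arm:

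d = (1.96 + 0.8416)·√(2/169) = 0.305 SD of the change after V2.

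Let k be the SD of gain before V2 divided by the SD of gain after V2, and ρ their correlation. For total gain:

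SD(total)/SD(post) = √(1 + k² + 2ρk), and power ≈ Φ(2.80 / [SD(total)/SD(post)] − 1.96).

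With ρ = 0 (assumption):

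| k | SD(total)/SD(post) | Power | n per arm to restore 80% |
|---|---|---|---|
| 0.5 | 1.12 | 71% | 212 |
| 1.0 | 1.41 | 51% | 339 |
| 1.5 | 1.80 | 34% | 550 |
| 2.0 | 2.24 | 24% | 846 |

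Over k from 0.5 to 2.0 and ρ from −0.2 to 0.3, power runs from 78% to 20%. Error in the recalled weight would act like a larger k.

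**5. If the origin is V2.** The loss in step 4 disappears. The t-test still ignores V2 weight, the 6 to 15 weeks left, and the minimisation factors. If these covariates explain a share R² of the variance of change, adjusting for them multiplies the standard error by about √(1 − R²). The documents give no basis for a value of R².

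**The case against.** A reader might infer that the plan measures weight change over the whole pregnancy. The documents do not say so. The outcome's wording can equally mean the antenatal phase as opposed to the time after delivery, and where section 2.2 speaks of body weight change it ties it to the study visits. The recalled weight also has another documented use, in the BMI class for minimisation.

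Nor is recalled weight the only starting value on offer. V1 weight is taken on calibrated scales, and weight is followed at every visit.

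A reader might also infer that any effect would be swamped. If variance of gain accrued evenly over 39 weeks, the standard error would be √(39/15) = 1.6 to √(39/6) = 2.5 times that of a change from V2. Nothing in the documents supports even accrual, and without SDs the loss runs from trivial to severe.

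Finally, the unadjusted comparison of randomised arms is valid. Earlier gain is balanced in expectation, and minimisation on gestational week at entry largely balances the time left to delivery.

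All of this stands, and it limits the point to precision and definition. It does not supply a start point or an end point. Balance between arms also does not remove within-arm variation from the standard error: a test that ignores prognostic minimisation factors tends to be conservative.

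**Conclusion.** The point holds as a low-cost improvement to one secondary outcome. The start and end of pregnancy weight change are undefined, and the stated test makes no use of weight or gestational week at randomisation.

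That most of gestation precedes V2 is firm: 62 to 85% with birth at 39 weeks, and at least 60% with birth at up to 40 weeks. The power loss is conditional on a preconceptional origin being chosen, and then on an SD ratio and a correlation that the documents do not give. Even in that case the result would be noisier, not biased. The gain from adjustment when change is taken from V2 cannot be quantified from the documents. The primary outcome and the sample size are not touched.

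**What to change.** In section 1.3, define pregnancy weight change as the last measured antenatal weight minus the measured weight at V2.

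In section 3.2, compare the arms by a linear model for this change with V2 weight, gestational week at V2, preconceptional BMI class and previous GDM as covariates. Report the adjusted mean difference in kg with its 95% confidence interval. Use gestational week at V2 for the time left, not the realised interval to delivery, because that interval is observed after randomisation and could be affected by treatment.

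Keep total gain from self-reported preconceptional weight as a descriptive figure.

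The cost is wording in two sections. Section 2.2 already has weight followed at every visit and the covariates recorded, so no new visit or measurement is needed. It specifies calibrated scales only for V1, so it should state that V2 weight is taken the same way.

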#### *1.4. Expected effects on the advancement of clinical practice*

The aim of this proposal is to assess the ability of rt-CGM to improve glycaemic control (reduction of mean glucose, hyperglycaemic episodes and duration, improvement of glycaemic variability) in order to prevent adverse pregnancy outcomes and neonatal complications in women with GDM. The results of this study will contribute to:

- the improvement of clinical monitoring and management of glucose metabolism during pregnancy with GDM
- increased knowledge about possible limitations of SMBG (routine care), such as undetected hyper- or hypoglycaemia, as well as to determine if comprehensive glucose data (as derived from CGM) results in more or fewer women needing pharmacotherapy
- possible improvement of adverse perinatal outcome and particularly fetal macrosomia in offspring of mothers with GDM

## 2. Research Design and Methods

### 2.1. Participants and recruitment; Exclusion criteria

This study is designed as an open-label multicentre randomized controlled trial with two parallel groups including a total of 372 female patients (n=186 with rt-CGM, n=186 with SMBG) with recent diagnosis of GDM. Diagnosis of GDM (i.e. diabetes first diagnosed in second and third trimester and not clearly type 1 or type 2 diabetes) is made in accordance with the IADPSG criteria after 24+0 weeks of gestation by a 2h 75g OGTT. If the GDM diagnosis is made before 24+0 weeks of gestation in accordance with the local guideline (i.e. when IADPSG cut-offs for fasting and post-load glucose are exceeded) patients can be included if no insulin treatment was started until 24+0^21. The study will be conducted at four tertiary referral centres in Austria, Switzerland, Sweden and Germany. All pregnant females (aged between 18 and 55 years) will be consecutively recruited after diagnosis of GDM until 31+6 weeks of gestation among women visiting the pregnancy outpatient departments (Division of Obstetrics and feto-maternal Medicine, Medical University of Vienna; Division of Obstetrics, University Hospital Basel, Clinic of Obstetrics, Charité Berlin, Clinic of Obstetrics, University Hospital Jena) or the diabetes outpatient departments (Division of Endocrinology and Metabolic Diseases at the Heinrich Heine University, Düsseldorf; Department of Medicine, University Hospital, Örebro).

Exclusion criteria are:

Overt diabetes (i.e. pregestationally known type 1 or type 2 diabetes or fasting plasma glucose during the OGTT  $\geq 126$  mg/dl [7.0 mmol/l] or HbA1c  $\geq 6.5\%$  [44 mmol/l] or 2h post-load OGTT levels  $\geq 200$  mg/dl [11.1 mmol/l] assessed before 24+0 weeks of gestation, whereby results need to be confirmed by repeated testing in case of unequivocal hyperglycemia according to the ADA standards); History of bariatric surgery or other surgeries that induce malabsorption; Long-term use (>2 weeks) of systemic steroids prior to enrolment; Multiple pregnancy; Patients already using glucose lowering medications (metformin or insulin) before study entry; fetal growth restriction due to placental dysfunction at study entry; Inpatient psychiatric treatment up to 1 year before enrolment; Participation in this study in previous pregnancy;

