### *2.3 Study visits postpartum*

Cord blood will be sampled and stored (at  $-80^{\circ}\text{C}$ ) immediately after delivery (VPP0). A postpartum examination will be scheduled within 48 hours after delivery (VPP1) for assessment of neonatal parameters and maternal HbA1c and glycosylated fibronectin, hsCRP, proBNP, Troponin T, (12 ml, non-fasting state), as well as between **8 weeks and 12 months** after delivery (VPP2) in all patients for a detailed re-examination of glucose homeostasis at postpartum (including lifestyle and dietary pattern as well as HbA1c, glycosylated Fibronectin, hsCRP, proBNP, Troponin T, as well as a blinded CGM for 10 days and an OGTT to assess the presence of prediabetic conditions after pregnancy with GDM). The postpartum OGTT is further used to provide estimates of insulin sensitivity,  $\beta$ -cell function and hepatic insulin extraction, the major physiological components of impaired glucose tolerance.

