### *2.13. Postpartum OGTT*

The OGTT will be performed at VPP2 (i.e. 8 – 16 weeks after delivery): after collecting blood samples for measurements of glucose (2 ml blood), insulin and C-peptide (3 ml blood) in the fasting state (at least 8 hours), participating females will receive a standardized 300 ml 75g glucose. Further blood samples of glucose, insulin and C-peptide measurements will be taken at 30, 60, 90, and 120 minutes. Insulin sensitivity during the OGTT will be assessed by the oral glucose insulin sensitivity index (OGIS) according to; this quantifies dynamic glucose

clearance per unit change of insulin. The more recently developed PREDIM index will be used in addition. As an approximation for hepatic insulin resistance the homeostasis model assessment of insulin resistance (HOMA-IR) will be used. Insulin secretion will be calculated by using the C-peptide deconvolution method.  $\beta$ -cell function parameters, such as pancreatic glucose sensitivity and rate sensitivity, and potentiation of insulin secretion, will be computed through mathematical modelling.

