#### 3.2. Analysis plan

Analyses should be conducted on the intention-to-treat principle. Categorical variables will be summarized by counts and proportions; continuous variables data will be summarized by means and standard deviations (SD) or by median and interquartile range in the case of strong deviations from the normal distribution. Pearson's chi-square test will be used to compare differences in the primary outcome (difference in proportion of LGA newborns) and for binary secondary outcomes (such as caesarean section rate, shoulder dystocia and neonatal hypoglycaemia). Bernard's test will be used as an alternative if an expected frequency in contingency tables is equal or less than 5 and the Cochran-Mantel-Haenszel method will be used as sensitivity analysis to adjust for possible center specific effects. Continuous secondary outcome parameters (such as mean glucose, duration and amount of hyperglycaemia, glycaemic variability and other CGM measures, postpartum OGTT data, HbA1c, glycosylated fibronectin, hsCRP, proBNP, Troponin T, or anthropometric data of the newborn) will be compared by student's t-test. Rank based inference (such as the Brunner-Munzel test) will be used as an alternative in case of skewed distributed parameters. The association between HbA1c, CGM measures and delivery and risk of LGA offspring will be assessed by binary logistic regression. There are many possible objectives for which analysis could be performed in this study (e.g. functional principal components analysis for CGM data). Hence, the present analysis plan represents only a selection of methods, which will be used for analysing the main objectives. Risk and time preferences will be analysed by non-parametric and parametric methods. In particular, we plan to fit the choice data to a CRRA (constant relative risk aversion) utility function. Associations between risk and time preferences and behaviour (dietary patterns and physical activity) will be investigated. For the health economic evaluation, incremental cost-effectiveness and cost-utility ratios (ICER/IUCR: additional cost per additional LGA

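### Pre-randomisation diagnostic glucose is not used as a covariate for the postpartum OGTT outcomes, which gives up precision on the long-term maternal metabolism hypothesis

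*Combined protocol and SAP*

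**What the plan says.** Section 1.2 hypothesises that rt-CGM "has beneficial long-term effects on maternal metabolism after pregnancy". Section 1.3 measures this by markers of insulin sensitivity, insulin secretion and beta-cell function from an OGTT after delivery. Section 2.3 adds that VPP2 includes "an OGTT to assess the presence of prediabetic conditions after pregnancy with GDM". Under section 2.13 "participating females will receive a standardized 300 ml 75g glucose", and glucose, insulin and C-peptide are sampled fasting and at 30, 60, 90 and 120 minutes.

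On the baseline side, section 2.1 says that the diagnosis "is made in accordance with the IADPSG criteria after 24+0 weeks of gestation by a 2h 75g OGTT". It also opens a second route, "If the GDM diagnosis is made before 24+0 weeks of gestation in accordance with the local guideline", which rests on fasting and post-load cut-offs. On either route the woman is recruited after diagnosis, and sections 2.2 and 2.4 place randomisation at V2.

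Section 3.2 assigns Student's t-test to continuous secondary outcomes, among them "glycaemic variability and other CGM measures, postpartum OGTT data, HbA1c, glycosylated fibronectin, hsCRP, proBNP, Troponin T, or anthropometric data of the newborn". The Brunner-Munzel test is named as an alternative for skewed data and the chi-square test covers binary outcomes. The only adjusted comparison of the arms is Cochran-Mantel-Haenszel for centre, as a sensitivity analysis. No baseline covariate is named for the arm comparison of any continuous outcome.

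**The concern.** A glucose measurement that cannot be affected by the allocated arm, and that plausibly predicts glucose metabolism after pregnancy, is left out of the comparison. The variation it would explain stays in the error term. These outcomes have no sample size calculation of their own, since section 3.1 sizes the trial on LGA alone, and VPP2 is the last visit, so attendance there may be lower than at delivery. What is at stake is the chance of detecting a moderate maternal benefit, and the width of the confidence interval around it.

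There is also a practical gap. The V1 data listed in section 2.2 do not include the diagnostic OGTT values. Unless their recording is specified, they may not reach the eCRF, and the adjusted analysis could not be done later.

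**Working it through.** **The plan's own figure.** Section 3.1 gives 169 per group for LGA proportions of 13.7% and 25.8%, two-sided alpha 0.05, power 80%. With pooled proportion 0.1975:

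n = [1.960 × √(2 × 0.1975 × 0.8025) + 0.842 × √(0.137 × 0.863 + 0.258 × 0.742)]² / 0.121² = 168.7, so 169.

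The figure reproduces. It concerns LGA only; the plan states no figure for the postpartum OGTT outcomes.

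**Is the covariate available before allocation?** Diagnosis requires glucose values, recruitment follows diagnosis, and randomisation is at V2. So it is, on both diagnostic routes.

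**Gain from adjustment.** Assumptions not in the documents: 150 women per arm with a VPP2 OGTT, and a correlation r between diagnostic glucose and the outcome of 0.2 to 0.5. ANCOVA multiplies the residual variance by 1 − r².

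- Detectable difference at 80% power, in SD units: (1.95996 + 0.84162) × √(2/150) × √(1 − r²) = 2.80158 × 0.11547 × √(1 − r²).
- Power at 0.30 SD: noncentral t with 298 degrees of freedom and noncentrality 0.30 × √(150/2) / √(1 − r²).
- Unadjusted sample size with the same precision: 150 / (1 − r²) per arm.

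| r | √(1 − r²) | Detectable difference (SD) | Noncentrality | Power at 0.30 SD | Equivalent unadjusted n per arm |
|---|---|---|---|---|---|
| 0 | 1.000 | 0.323 | 2.598 | 73.6% | 150 |
| 0.2 | 0.980 | 0.317 | 2.652 | 75.3% | 156 |
| 0.3 | 0.954 | 0.309 | 2.724 | 77.5% | 165 |
| 0.5 | 0.866 | 0.280 | 3.000 | 84.9% | 200 |

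**Sensitivity to attendance.** With all 169 per group evaluable, the unadjusted detectable difference is 0.305 SD, falling to 0.299, 0.291 and 0.264 SD for r of 0.2, 0.3 and 0.5. With 130 or 100 per group the unadjusted values are 0.347 and 0.396 SD. The relative gain is the same each time.

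**Cost of the covariate.** With 338 women, one covariate inflates the variance by about 1/334 = 0.3%. Adjustment therefore pays once |r| exceeds about √(1/335) = 0.05.

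**Which outcomes have a matching baseline?** At VPP2 glucose, insulin and C-peptide are all measured. For the diagnostic test the documents imply glucose only. OGIS, PREDIM, HOMA-IR, insulin secretion and the beta-cell measures need insulin or C-peptide, so they have no pre-randomisation counterpart.

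**The case against.** The strongest reply is that the gain may be small. The two tests are separated by treatment, delivery and up to 12 months on the window in section 2.3. (Section 2.13 gives 8 to 16 weeks; the two should be reconciled.) All women were selected for exceeding a cut-off, which may narrow the baseline range and lower the correlation. At r = 0.2 the gain is 0.006 SD and under two points of power. Most named outcomes are not glucose values. Section 3.2 also calls itself a selection of methods, so adjustment is not excluded. All of this stands and limits the size of the point. It does not remove it: the cost is close to nil, and a covariate chosen after the data are seen is open to a charge of selection.

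A reader might infer three stronger things that the documents do not support.

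- That the unadjusted test is biased because severity of GDM may differ by chance between arms. It is not: randomisation balances severity in expectation, and the test's type 1 error already allows for chance imbalance. Minimisation on BMI class, previous GDM and gestational week may balance part of it as well.
- That adjustment would remove bias from selective attendance at VPP2. Attendance that depends on severity equally in both arms does not in general bias the difference. If the dependence differs by arm, adjustment helps only so far as the recorded covariates explain attendance and the model is right. Nothing in the documents shows this.
- That the overt-diabetes exclusion proves sites hold values from the test after 24+0. It does refer to "fasting plasma glucose during the OGTT", but its later qualifier about testing before 24+0 can be read as limiting it to early tests. The point does not need this, because diagnosis itself requires the values.

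**Conclusion.** The point holds as a modest loss of efficiency in secondary outcomes. The planned tests are valid and the primary LGA analysis is unaffected. Under the assumed correlations of 0.2 to 0.5, variance falls by 4% to 25%, which is slight at the low end and worthwhile at the high end. The upper part of that range is more plausible for postpartum glucose than for the insulin and C-peptide indices. Both the correlation and the 150 per arm are assumptions. The calculation covers continuous outcomes only and says nothing about prediabetes as a binary outcome. This is a desirable improvement that the trial can do without.

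**What to change.** 1. Record in the eCRF the diagnostic fasting and post-load glucose values and the date of the test.
2. In section 3.2, prespecify ANCOVA for continuous postpartum OGTT outcomes, with arm, diagnostic fasting glucose, diagnostic 2-h glucose and preconceptional BMI in the model. BMI class is already a minimisation factor under section 2.4, so including BMI also lets the analysis reflect the balance that the allocation method seeks.
3. HbA1c at V2, already scheduled in section 2.2, may be added, or used where diagnostic glucose is missing.
4. State a transformation rule for skewed outcomes, and a rule for baselines that are missing or were taken before 24+0.
5. Keep the unadjusted t-test and rank test as sensitivity analyses.
6. If prediabetes is analysed by covariate-adjusted logistic regression, also report a marginal risk difference, because the adjusted odds ratio is a conditional measure.

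The cost is two or three existing numbers and a date per woman, plus a few sentences in the SAP. No new test is needed. The real work is the handling rule for women diagnosed before 24+0, whose test was done at another gestational age and who may lack one of the values.
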